## **6.5 Environmental Assessment**

A claim is made for categorical exclusion under 21 CFR 25.31 (e) for this IND. The use of ALA is not considered toxic and the standard procedure for chemotherapy waste disposal will followed.

## **7 STATISTICAL CONSIDERATIONS**

### **7.1 Study Endpoints**

This is a single-center, single arm, open label phase II trial of fluorescence-guided resection by use of 5-aminolevulinic (ALA) at a dose of 20 mg/kg body weight in glioma patients. We hypothesize that surgical removal of the residual fluorescent tissues in the tumor cavity, presumably representing tumorous cells, will result in an increase in the amount of tumor removal during neurosurgical resection. In addition, we hypothesize that for recurrent malignant glioma, that the fluorescent material will reflect active viable tumor and not changes related to treatment such as macrophages or gliosis.

The primary analysis will be based on one biopsy taken from the most fluorescent area and one from normal appearing tissues for each patient as judged by the neurosurgeon.

The endpoints of interest in this study are as follows:

- Primary Endpoint: Positive Predictive Value (PPV), defined as the percentage of biopsies taken from the most fluorescent tissues determined by the pathologist as having tumorous content.
- Second Endpoints:
  - Negative Predictive Value (NPV), defined as the percentage of biopsies taken from non-fluorescent tissues determined as having no tumor content by the pathologist.
  - The safety of the use of 5-aminolevulinic (ALA) at a dose of 20 mg/kg body weight for neurosurgical resection in glioma patients
  - The correlation between fluorescent intensity as scored by the neurosurgeon and the tumor content as scored by the pathologist
  - The percentage of patients for whom there is no fluorescent tissue after surgery

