### 5.2 Surgical Procedure

ALA will be mixed in the minimum volume of sterile water or juice immediately before use and given as a single bolus orally approximately 3 hours prior to scheduled anesthesia. Image-guided microsurgical resection of the tumor will be undertaken. Following the standard tumor resection under light microscopy, the residual tumor bed will be illuminated with blue light via a high pass optical filter in the microscopes light chain. The surgeon will examine the tumor bed with a barrier filter in the optical chain of the surgical microscope. The surgeon will quantitatively measure the concentration of Pp IX by placing the intraoperative fluorescence/reflectance probe in gentle contact with brain tissue by the surgeon for 3-5 seconds to make a recording. If fluorescence is present, and if safe, small biopsies will be taken from those areas of fluorescence as well as from non-fluorescing regions in the tumor resection cavity. When possible, the intent would be to collect a number of biopsies with a range of fluorescence intensities from each patient (at least one biopsy from normal-appearing tissues and at least one from the most fluorescent area). All biopsy specimens, including those taken from the bulk tumor, will be reviewed by a neuropathologist to assess tumor content. The expectation is that residual fluorescent tissue in the tumor cavity will be surgically removed (if deemed safe by the

neurosurgeon), potentially leading to more complete tumor resection. Pathologic confirmation of tumor type will be made by neuropathology.

Biopsies of fluorescent and non-fluorescent tissue within the tumor cavity will be graded by the surgeon at the time of biopsy as 0 to 3 fluorescence. A screen shot of the fluorescent image of the resected tumor illuminated with blue light via a high-pass filter will be documented for each patient with an integrating video camera. The fluorescence intensity and the quantitative measurement obtained with the intraoperative probe corresponding to each area on the screen shot from which biopsy is taken will be recorded by the surgeon in the operating room. The sample will be snap frozen in the operating room and provided to the pathologist for grading the tumor from 0 to 3 based on the degree of cellular infiltration. The scale to be used for grading is as follows:

Grade	Surgeon (intensity of fluorescence)	Pathologist (cell density)
0	No fluorescence	No tumor cell density content

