1	Mild brightness	Mildly infiltrating tumor cell density
2	Moderate brightness	Moderately infiltrating cell density
3	Intense brightness	Highly infiltrating cell density

The surgeon is responsible for:

- Identifying at least one fluorescent area within the tumor cavity and performing biopsy and grading that site's fluorescence.
- Identifying at least one non-fluorescent area within the tumor cavity and performing biopsy and grading that site's fluorescence.
- Labeling the areas (i.e. fluorescent or non-fluorescent) from which the biopsies are taken.

The pathologist is responsible for:

- Grading each frozen section biopsy for tumor content on a scale of 0 to 3.
- Labeling of specimens to be certain they correlate with biopsies taken by the surgeon.

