## 7.2 Sample Size Determination

There is interest in assessing the correlation of 5-ALA uptake and degree of fluorescence among the different grades and histological subtypes of newly diagnosed high- and low- grade glioma. In addition, once a high-and low- grade glioma has been treated with radiation and chemotherapy, it is well accepted that treatment related changes can be seen histologically. There has been little experience in the assessment of the use of 5-ALA in the recurrent setting and in this study we are interested in the specificity of 5-ALA uptake in tumor cells in the post treated setting. As such, in addition to newly diagnosed glioma patients, there will be a specific subgroup of recurrent glioma who will be studied.

The patients will be allocated to the following subgroups:

- 1) Newly diagnosed GBM
- 2) Newly diagnosed grade III glioma (astrocytic, oligodendroglial and mixed)
- 3) Recurrent GBM
- 4) Recurrent grade III glioma (astrocytic, oligodendroglial and mixed)
- 5) Newly diagnosed low grade glioma (astrocytic, oligodendroglial, ganglioglioma, and mixed)
- 6) Recurrent low grade glioma (astrocytic, oligodendroglial, ganglioglioma, and mixed)

A total of 50 patients per subgroup will be enrolled. The main goal is to determine the intraoperative detection of malignant and low grade glioma by the use of 5-aminolevulinic (ALA), as measured by PPV defined above. In order for this agent to be useful, we would expect PPV to be at least 80%. Therefore, 80% is considered the lower threshold for the hypothesis testing (i.e. under H0). The calculation of sample size was based on a targeted PPV of 92%. Fifty patients per cohort will provide approximately 90% power to detect this improvement using a one-sided exact binomial test with alpha of 0.10. The agent will be deemed useful if 44 or more biopsies taken from the most fluorescent tissues are determined by the pathologist as having tumorous content.

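### In recurrent malignant glioma, PPV tests the viable-tumour hypothesis only in part: biopsies mixing tumour cells with treatment change count as successes, and treatment change is not recorded

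*Combined protocol and SAP*

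**What the plan says.** Besides its general hypothesis about the amount of tumour removed, section 7.1 gives a separate one for recurrent malignant glioma: "the fluorescent material will reflect active viable tumor and not changes related to treatment such as macrophages or gliosis". Section 7.2 justifies the recurrent patients by noting that treatment leaves changes visible on histology and that experience with the agent in recurrence is limited. It adds that "we are interested in the specificity of 5-ALA uptake in tumor cells in the post treated setting". Subgroups 3 and 4 are recurrent GBM and recurrent grade III glioma, and subgroup 6 is recurrent low grade glioma. Each has 50 patients.

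In section 5.2 the pathologist's listed duties are "Grading each frozen section biopsy for tumor content on a scale of 0 to 3" and matching specimen labels to the surgeon's biopsies. Grade 0 is "No tumor cell density content", grade 1 is "Mildly infiltrating tumor cell density" and grade 2 is "Moderately infiltrating cell density". Grade 3, like grade 2, omits the word tumour.

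The primary endpoint, PPV, is "the percentage of biopsies taken from the most fluorescent tissues determined by the pathologist as having tumorous content". Section 7.2 states that "80% is considered the lower threshold for the hypothesis testing", sets a target of 92%, and calls the agent useful at 44 or more positive biopsies, with 50 patients per cohort. Sections 7.1 to 7.3 contain no item on viability, macrophages, gliosis or necrosis, and no analysis specific to the recurrent cohorts.

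**The concern.** The hypothesis contrasts two kinds of tissue, viable tumour and treatment-related change. The measurement records only how much tumour is present. After radiation and chemotherapy both can lie in one small biopsy, and the plan has no field that describes such a sample. Read naturally, any grade of 1 or higher is tumour content, so a mixed biopsy is a PPV success whatever its balance.

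At stake is what a positive result in the recurrent cohorts can be said to show. It would show that tumour cells were usually present where fluorescence was brightest. It would not show whether that tissue was mainly active tumour, which is what the hypothesis asserts. If the item is not recorded prospectively, answering the question later would need a re-review of specimens that the plan does not provide for.

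**Working it through.** **1. The plan's own figure.** Inputs from section 7.2: n = 50, rule 44 or more, null PPV 0.80, target PPV 0.92, one-sided exact binomial test, nominal alpha 0.10, power about 90%. With X ~ Binomial(50, p):

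- P(X ≥ 44 | p = 0.92) = 0.898, so the stated power reproduces.
- P(X ≥ 44 | p = 0.80) = 0.1034, slightly above the nominal 0.10. This is a separate matter and does not affect the present point.

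**2. How each kind of fluorescent biopsy is counted**, taking grade 1 or higher as tumour content:

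| Content of the most-fluorescent biopsy | Grade | PPV | Bearing on the hypothesis |
|---|---|---|---|
| Mainly viable tumour | 1 to 3 | success | supports |
| Some tumour cells, mainly treatment change | 1 or higher | success | not shown |
| Tumour cells present, viability in doubt | 1 or higher | success | not shown |
| Macrophages or gliosis only | 0 | failure | contradicts |

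PPV agrees with the hypothesis in the first and last rows and says nothing about it in the middle two.

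**3. Whether the middle rows could change a decision.** Let v be the true share of most-fluorescent biopsies that are mainly viable tumour. Let q be the share of the remainder still scored as having tumour content. The PPV that the rule sees is p = v + q(1 − v), and the chance of passing is P(X ≥ 44 | p). The documents give neither v nor q, so every value below is an assumption.

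| v | q = 0 | q = 0.25 | q = 0.5 | q = 0.75 |
|---|---|---|---|---|
| 0.70 | 0.3% (p = 0.70) | 4.7% (p = 0.775) | 36.1% (p = 0.85) | 92.2% (p = 0.925) |
| 0.80 | 10.3% (p = 0.80) | 36.1% (p = 0.85) | 77.0% (p = 0.90) | 98.8% (p = 0.95) |

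At v = 0.70, the counted PPV reaches the 92% target when q = (0.92 − 0.70)/(1 − 0.70) = 0.73.

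The column q = 0 is the case where everything that is not mainly viable tumour is free of tumour cells. There the rule does its job. It weakens as q rises, and q is not recorded.

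**4. A counting example (assumed mixes).** Of 50 biopsies, 4 have no tumour, so PPV is 46/50 = 92% and the cohort passes. If 20 are mainly viable tumour and 26 are mixed, the mainly viable share is 20/50 = 40%. If 35 are mainly viable and 11 mixed, it is 35/50 = 70%. PPV is the same in both.

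**The case against.** The strongest reply is that PPV already tests the main content of the hypothesis. Fluorescent tissue made up only of macrophages or gliosis has no tumour cells, is graded 0 and counts against the 44. If 30% of a cohort's biopsies were of that kind, it would pass only 0.3% of the time. This stands. A reader might infer that the recurrent hypothesis goes wholly untested, and the documents do not support that.

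A reader might also infer that the plan has no means of separating the two mixes in the counting example. That goes too far. The 0 to 3 grade is kept for every biopsy, and its relation to fluorescence intensity is a secondary endpoint analysed by rank correlation and a Cochran-Mantel-Haenszel test. If mixed biopsies are mostly grade 1 and mainly viable ones grade 2 or 3, the grade distributions would differ. The separation is only partial, because the grade measures infiltrating cell density and not viability or the amount of treatment change.

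The word specificity in section 7.2 may suggest a promised diagnostic specificity that fluorescence-selected biopsies cannot supply. The sentence concerns uptake in tumour cells, that is, selectivity, which is also how section 3 uses the word when discussing fluorescein. No true-negative rate is planned, so no analysis fails on that account.

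Three further replies stand. The size of the effect rests on assumed shares. No section says that a high PPV will be read as proof of the viable-tumour hypothesis; section 7.2 ties the rule to intraoperative detection of glioma. And a slide shows what the tissue contains, not which cells fluoresced.

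**Conclusion.** The point holds in a limited form. For recurrent malignant glioma, PPV answers the hypothesis where fluorescent tissue has no tumour cells. It leaves open the biopsies that mix tumour cells with treatment change, and it leaves viability unmeasured. A recurrent cohort could meet the 44-of-50 rule without showing whether the fluorescent tissue was mainly viable tumour.

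How often this would happen cannot be computed from the documents. The range of 0.3% to 92% at v = 0.70 shows only that the outcome depends on a quantity the trial will not record. The conclusion assumes that grade 1 or higher counts as tumour content, which the plan implies but does not state.

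The hypothesis as worded covers subgroups 3 and 4, 2 × 50 = 100 patients. Extending it to all 150 recurrent patients is not supported by section 7.1; subgroup 6 comes in only through the broader interest expressed in section 7.2.

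A smaller matter belongs here. Because grades 2 and 3 drop the word tumour, dense reactive tissue could, on a literal reading, be graded 2 or 3. The pathologist's duty to grade tumour content points the other way, and the two should be made to agree.

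**What to change.** - **Section 5.2.** For subgroups 3 and 4, and optionally 6, have the same pathologist record on the same biopsy whether treatment-related change (gliosis, macrophages, necrosis) is absent, present or predominant, and whether viable tumour is present. Define predominant in advance. Word grades 2 and 3 as tumour cell density, like grades 0 and 1.
- **Sections 7.1 and 7.3.** Add a secondary descriptive measure for these cohorts: the proportion of most-fluorescent biopsies with viable tumour and without predominant treatment change, with a 95% CI, reported beside PPV. Say which grades count as tumour content for PPV. State that the new measure describes the composition of the fluorescent tissue and does not show which cells fluoresced.
- **Unchanged.** PPV as the primary endpoint, 50 patients per cohort and the 44-of-50 rule.

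The cost is a short addition to the pathology form for about 100 patients (150 with subgroup 6) and one more proportion in the report. No extra patients are needed. The documents do not show how reliably these features can be read on frozen section, so the pathologist should confirm this before the form is fixed. The recurrent-cohort figure may also be less favourable than PPV.

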## 7.2 Sample Size Determination

There is interest in assessing the correlation of 5-ALA uptake and degree of fluorescence among the different grades and histological subtypes of newly diagnosed high- and low- grade glioma. In addition, once a high-and low- grade glioma has been treated with radiation and chemotherapy, it is well accepted that treatment related changes can be seen histologically. There has been little experience in the assessment of the use of 5-ALA in the recurrent setting and in this study we are interested in the specificity of 5-ALA uptake in tumor cells in the post treated setting. As such, in addition to newly diagnosed glioma patients, there will be a specific subgroup of recurrent glioma who will be studied.

The patients will be allocated to the following subgroups:

- 1) Newly diagnosed GBM
- 2) Newly diagnosed grade III glioma (astrocytic, oligodendroglial and mixed)
- 3) Recurrent GBM
- 4) Recurrent grade III glioma (astrocytic, oligodendroglial and mixed)
- 5) Newly diagnosed low grade glioma (astrocytic, oligodendroglial, ganglioglioma, and mixed)
- 6) Recurrent low grade glioma (astrocytic, oligodendroglial, ganglioglioma, and mixed)

A total of 50 patients per subgroup will be enrolled. The main goal is to determine the intraoperative detection of malignant and low grade glioma by the use of 5-aminolevulinic (ALA), as measured by PPV defined above. In order for this agent to be useful, we would expect PPV to be at least 80%. Therefore, 80% is considered the lower threshold for the hypothesis testing (i.e. under H0). The calculation of sample size was based on a targeted PPV of 92%. Fifty patients per cohort will provide approximately 90% power to detect this improvement using a one-sided exact binomial test with alpha of 0.10. The agent will be deemed useful if 44 or more biopsies taken from the most fluorescent tissues are determined by the pathologist as having tumorous content.

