### 7.3 Statistical Analysis

The primary analysis will include all patients who are eligible for this study and who undergo planned neurosurgery. PPV and NPV will be estimated and the 95% confidence interval associated with each measure will be provided. Secondary analysis will take advantage of multiple biopsies taken from areas representing a range of fluorescence intensity within each patient. The Spearman's rank correlation coefficient will be calculated to assess the correlation between fluorescent intensity as scored by the neurosurgeon and the tumor content as scored by the pathologist. To account for within-patient correlation, the Cochran-Mantel-Haenszel Chi-Squared test will be used to test the association between fluorescence intensity and tumor content.

All patients who are enrolled and take 5-ALA will be considered evaluable for toxicity. Since potential adverse events related to 5-ALA are known to be transient in nature, it is felt that a 14-day evaluation window is relevant to assess the safety profile of this agent. The formal analysis and final report of toxicities will be performed when all patients have been enrolled and followed for toxicities for 14 days after administration of 5-ALA. Reporting of adverse events is described in Section 6. We intend to monitor adverse events on a monthly basis to determine if there are unacceptable toxicities. A report of all adverse events since the first subject was enrolled will be prepared every month, along with a tabular display of the relative frequency of all grade 2 or higher toxicities considered possibly, probably, or likely related to 5-ALA. This information will be submitted to the UCSF-CCC Data Safety Monitoring Committee (DSMC) who is responsible for monitoring data quality and patient safety for all UCSF-CCC institutional clinical studies.

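### The success rule of 44 or more out of 50 has an exact one-sided type I error of 0.1034, slightly above the alpha of 0.10 stated for it.

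*Combined protocol and SAP*

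**What the plan says.** Section 7.2 of the combined protocol and SAP gives every element of the primary decision rule.

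- **Size:** "A total of 50 patients per subgroup will be enrolled".
- **Null value:** "80% is considered the lower threshold for the hypothesis testing".
- **Alternative:** "The calculation of sample size was based on a targeted PPV of 92" percent.
- **Test, level and power:** "Fifty patients per cohort will provide approximately 90% power to detect this improvement using a one-sided exact binomial test with alpha of 0.10".
- **Decision rule:** "The agent will be deemed useful if 44 or more biopsies taken from the most fluorescent tissues" are found by the pathologist to contain tumor.

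Section 7.1 bases the primary analysis on one biopsy per patient from the most fluorescent area, so a complete subgroup has a denominator of 50. Section 7.3 names no test for the primary endpoint. It says only that "PPV and NPV will be estimated and the 95% confidence interval associated with each measure will be provided". The count in Section 7.2 is therefore the only stated criterion for success.

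**The concern.** An exact binomial test at alpha 0.10 is normally understood to have a type I error no greater than 0.10. Because the binomial distribution is discrete, few error rates are attainable at n = 50, and the cut-off of 44 falls just on the wrong side of that limit. The word approximately in Section 7.2 qualifies the power and not the alpha, and no attained type I error is reported.

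At stake is the accuracy of the error rate given for the primary decision rule. Read side by side, two sentences of Section 7.2 also disagree on one possible result. At exactly 44 of 50, the rule declares the agent useful and the named test does not reject at 0.10.

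**Working it through.** **Inputs (Sections 7.1 and 7.2).** n = 50 biopsies, one per patient; null PPV p0 = 0.80; target PPV p1 = 0.92; one-sided exact binomial test, alpha 0.10; cut-off r = 44; stated power about 90%.

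**Formula.** For X distributed Binomial(n, p), P(X ≥ r | n, p) = Σ from k = r to n of C(n, k) p^k (1 − p)^(n − k). The type I error is this tail at p0, and the power is the same tail at p1.

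**Step 1: the plan's power.** P(X ≥ 44 | 50, 0.92) = 0.8981. The stated figure of about 90% is reproduced.

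**Step 2: the type I error of the same rule.** The terms at p = 0.80 are:

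| k | P(X = k) |
|---|---|
| 44 | 0.05537 |
| 45 | 0.02953 |
| 46 | 0.01284 |
| 47 | 0.00437 |
| 48 | 0.00109 |
| 49 | 0.00018 |
| 50 | 0.00001 |

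Their sum, before rounding of the terms, is P(X ≥ 44 | 50, 0.80) = 0.10340. The excess over the stated level is 0.1034 − 0.10 = 0.0034.

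**Step 3: the cut-off that keeps the type I error at or below 0.10.** Dropping the term for 44 gives 0.10340 − 0.05537 = 0.04803, so 45 is the smallest cut-off that qualifies. Its power is P(X ≥ 45 | 50, 0.92) = 0.7919.

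| Cut-off at n = 50 | Type I error at 80% | Power at 92% |
|---|---|---|
| 44 or more | 0.1034 | 0.898 |
| 45 or more | 0.0480 | 0.792 |

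The stated power belongs to the first row, and a strict alpha of 0.10 allows only the second. No cut-off at n = 50 gives both.

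**Step 4: other ways of reaching 0.10.** For 44 of 50, a normal approximation gives 0.0786 without and 0.1080 with continuity correction, and the mid-p value is 0.0757. None equals 0.10, and the plan names the exact test in any case.

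**Step 5: when the difference shows.** The rule and the exact test at 0.10 disagree only at X = 44, where the one-sided p-value is 0.1034. The chance of that result in one subgroup with 50 evaluable biopsies is:

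| True PPV | P(X = 44) |
|---|---|
| 80% | 5.5% |
| 85% | 14.2% |
| 90% | 15.4% |
| 92% | 10.6% |

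**Step 6: dependence on the denominator.** Section 5.2 makes the fluorescent biopsy conditional: "If fluorescence is present, and if safe, small biopsies will be taken from those areas of fluorescence". If the count of 44 stays fixed while fewer biopsies are evaluable:

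| Evaluable | Type I error, 44 or more | Power, 44 or more | Smallest cut-off with type I error ≤ 0.10 |
|---|---|---|---|
| 50 | 0.1034 | 0.898 | 45 |
| 49 | 0.0547 | 0.805 | 44 |
| 48 | 0.0248 | 0.662 | 43 |

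The excess over 0.10 therefore arises only with the full 50. At 49 the rule and the exact test coincide. At 48 the rule is stricter than the test.

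**The case against.** The best reply is that this is rounding. The plan gives alpha to two decimals, and 0.1034 rounds to 0.10. Section 7.2 does not call 0.10 a ceiling. Read as a description of one design, its figures all reproduce to the precision given. The excess is also tiny: the rule's rejection probability equals 0.10 at a true PPV of 79.89%, so it amounts to moving the null value by about 0.11 percentage points, and 80% is itself a round figure. No test is planned in Section 7.3, so the clash at 44 of 50 appears only if someone runs one. Finally, Section 3.4 says that visible fluorescence is limited in lower grade gliomas. Some subgroups may then fall short of 50 fluorescent biopsies, in which case the rule is conservative and the loss is in power.

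Most of this stands as an argument about weight. The excess is negligible for a phase 2 decision, the percentages for exactly 44 of 50 are not chances of a wrong decision, and the effect of a smaller denominator on power is larger than the excess in alpha. It does not remove the inconsistency. The plan names an exact test, whose usual meaning is a type I error at or below the stated level, and it qualifies only the power as approximate. That the count governs is a reason to state the count's own error rate correctly.

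**Conclusion.** The concern holds, as a minor point. With 50 evaluable biopsies in a subgroup, the 44-or-more rule has a type I error of 0.1034 against the stated 0.10, while its power of 0.898 is as stated. What is wrong is the error rate attached to the rule. The rule itself and the sample size are not in question.

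This rests on three assumptions: one most-fluorescent biopsy per patient, independent results across patients, and all 50 biopsies evaluable. It concerns each subgroup separately and says nothing about error across the six subgroups.

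**What to change.** In Section 7.2, keep the cut-off and replace the nominal alpha by the attained error rates. Suggested wording:

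> With 50 evaluable biopsies from the most fluorescent tissue in a cohort, the agent will be deemed useful if 44 or more contain tumor. This count is the decision criterion; its exact one-sided type I error is 0.103 at a PPV of 80% and its power is 0.898 at a PPV of 92%.

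The cost is one or two sentences, with no change to the rule, the number of patients or the power. The wording also names the denominator, which the present success sentence leaves out. It does not say what applies when fewer than 50 are evaluable; the cut-offs in Step 6 of the working could be added for that.

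If the sponsor prefers a type I error strictly at or below 0.10, there are two alternatives. One is 45 of 50, with a type I error of 0.048 and power of 0.792. The other is 45 of 51, with 0.092 and 0.890, at the cost of one more patient per subgroup (6 × 1 = 6 in all). For an excess of 0.0034, restating the error rate is enough.

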### **3.4 Rationale for the Intraoperative Fluorescence/Reflectance Probe**

Although ALA results in visible concentrations of Pp IX in high grade malignant gliomas, detection in lower grade gliomas is limited due a relatively low intensity of fluorescence signals, resulting in incomplete tumor detection. However, Pp IX does accumulate to diagnostically significant levels in low grade gliomas even when not visibly evident to the

surgeon (21). To aid in the quantitative detection of subvisual concentrations of Pp IX in low grade gliomas, an intraoperative fluorescence/reflectance probe was custom designed under NIH funding. The intraoperative probe is a 1.25 mm semi-rigid, blunt end device that is placed in gentle contact with brain tissue by the surgeon for 3-5 seconds to make a spectroscopic measurement. The probe delivers a very small amount of blue light and white light to measure the concentration of Pp IX.

The probe meets all of the criteria necessary for classification as a non-significant risk device according to FDA guidelines. The device is non-invasive with respect to the participant and does not present a serious risk to the health, safety, or welfare of a subject. The device is not used to diagnose, cure, mitigate, or treat disease without concordance from additional data made available through practices which meet or exceed standard-of-care. The light exposure levels are below those known to cause any temperature rise or other significant tissue damaging effects, even in conjunction with ALA which can be phototoxic but at much higher light exposure thresholds.

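### The success count of 44 positive biopsies fits the named exact test only at 49 fluorescent-site biopsies; below 49 it loses power, and at 50 its exact alpha is 0.103

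*Combined protocol and SAP*

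**What the plan says.** Section 7.2 plans 50 patients in each of six subgroups, with a null PPV of 80% and a target of 92%. It says: "Fifty patients per cohort will provide approximately 90% power to detect this improvement using a one-sided exact binomial test with alpha of 0.10". It then gives the decision rule: "The agent will be deemed useful if 44 or more biopsies taken from the most fluorescent tissues" are found by the pathologist to contain tumor. That sentence has no denominator, proportion or scaling; 50 per subgroup is the reading from context.

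The documents differ on whether every patient supplies such a biopsy.

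- Section 7.1 bases the primary analysis on one most-fluorescent biopsy and one from normal-appearing tissue per patient. The list of surgeon's duties in section 5.2 includes finding and sampling at least one fluorescent area. Both imply 50 biopsies.
- The procedure in section 5.2 is conditional. "Following the standard tumor resection under light microscopy, the residual tumor bed will be illuminated with blue light", and then "If fluorescence is present, and if safe, small biopsies will be taken from those areas of fluorescence". The wider biopsy set is an intent, to be met when possible.
- Section 3.4 says that visible "detection in lower grade gliomas is limited due a relatively low intensity of fluorescence signals". It adds that Pp IX still accumulates below the visible level and that a probe was built to measure it.

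On the denominator, section 7.1 has PPV "defined as the percentage of biopsies taken from the most fluorescent tissues determined by the pathologist as having tumorous content", which is per biopsy. Section 7.3 says "The primary analysis will include all patients who are eligible for this study and who undergo planned neurosurgery", which is per patient.

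**The concern.** A count of 44 has the stated operating characteristics only if the denominator is 50. With fewer fluorescent-site biopsies, the same count demands a higher observed PPV, and beyond a point it cannot be met at all. The written rule and the test named one sentence before it could then give opposite verdicts on the same data, for the primary endpoint. The condition in section 5.2 applies to all six subgroups. Section 3.4 makes the concern most plausible in the two low-grade subgroups, which face the same count.

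The secondary endpoint on absent fluorescence does not settle how such patients count. It is "The percentage of patients for whom there is no fluorescent tissue after surgery", so it pools patients who never fluoresced with those whose fluorescent tissue was removed.

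**Working it through.** **Inputs (section 7.2).** n = 50 per subgroup, null PPV 0.80, target PPV 0.92, one-sided exact binomial test, alpha 0.10, success count 44. The number of fluorescent-site biopsies m is not given, so a range is used.

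**Step 1: reproduce the plan.**
- Power: P(Bin(50, 0.92) ≥ 44) = 0.898, which agrees with about 90%.
- Type I error: P(Bin(50, 0.80) ≥ 44) = 0.1034, slightly above 0.10.
- With 45 of 50: alpha 0.048 and power 0.792.

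So at m = 50 no count gives both alpha of at most 0.10 and power of about 90%.

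**Step 2: fixed count against re-derived cut-off.** The fixed count succeeds with probability P(Bin(m, 0.92) ≥ 44). The re-derived cut-off is the smallest r with P(Bin(m, 0.80) ≥ r) ≤ 0.10, and its power is P(Bin(m, 0.92) ≥ r).

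| m | Observed PPV needed, 44/m | Fixed 44: alpha | Fixed 44: power | Re-derived r | Alpha | Power |
|---|---|---|---|---|---|---|
| 50 | 88.0% | 0.103 | 0.90 | 45 | 0.048 | 0.79 |
| 49 | 89.8% | 0.055 | 0.80 | 44 | 0.055 | 0.80 |
| 48 | 91.7% | 0.025 | 0.66 | 43 | 0.062 | 0.82 |
| 47 | 93.6% | 0.009 | 0.48 | 42 | 0.070 | 0.83 |
| 46 | 95.7% | 0.003 | 0.28 | 41 | 0.080 | 0.84 |
| 45 | 97.8% | 0.0005 | 0.12 | 40 | 0.090 | 0.85 |
| 44 | 100% | 0.00005 | 0.03 | 40 | 0.044 | 0.73 |
| 40 | not attainable | 0 | 0 | 36 | 0.076 | 0.79 |
| 35 | not attainable | 0 | 0 | 32 | 0.061 | 0.69 |
| 30 | not attainable | 0 | 0 | 28 | 0.044 | 0.57 |

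The fixed count cannot be met at any m of 43 or fewer. At m = 49 the two cut-offs are the same, so harm specific to the fixed count starts at m = 48. At m of 10 or fewer the exact test cannot reject either, since 0.8^10 = 0.107.

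**Step 3: examples of opposite verdicts.**
- 43 of 45 fails the count, but P(Bin(45, 0.80) ≥ 43) = 0.003.
- 40 of 40 fails the count, but 0.8^40 = 0.0001, and the exact 95% CI is 91.2% to 100%.

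**Step 4: the other possible denominator.** Suppose a patient without a fluorescent-site biopsy counts as a non-success among 50, and a fraction f yields one. Power is then P(Bin(50, 0.92f) ≥ 44): 0.78, 0.56, 0.22 and 0.01 at assumed f of 98%, 95%, 90% and 80%.

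**The case against.** The best defence is that the plan expects 50 biopsies. Section 7.1 and the surgeon's duties in section 5.2 both call for one fluorescent biopsy from each patient, and the probe described in section 3.4 exists because visible fluorescence is weak in low-grade tumors. This stands as evidence of intent, but it does not override the condition in the same section 5.2. No text says that a probe reading can define the most fluorescent site, and the surgeon's 0 to 3 grade is one of brightness. If the most fluorescent area could have grade 0, PPV would include non-fluorescent tissue.

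A second defence is that section 7.3 includes all eligible operated patients, so a patient with no fluorescent biopsy is in effect a non-success. On that view 40 positives in 50 patients is 40/50 = 80%, the null value, and failing is coherent. This reading is possible, but it sits badly with the per-biopsy definition in section 7.1, is nowhere stated, and carries the power in step 4.

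A third is that 44 is simply the cut-off for the planned n, the exact test is named beside it, and section 7.3 reports PPV with a 95% CI. An analyst could re-derive the cut-off, and a high PPV would be visible. That limits the damage, but the choice would be made after the data were seen.

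Three stronger readings are tempting. A reader might infer that the low-grade subgroups are bound to fail; the documents give no rate of absent fluorescence, so that cannot be said. A reader might blame the fixed count for the fall in power from 0.90 to 0.80 at m = 49; the re-derived cut-off there is also 44. A reader might take a shortfall to raise the false-positive risk; with the count held at 44, type I error falls as m falls.

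**Conclusion.** The concern holds: the primary decision rule is wrong as written and should be fixed. If m is below 49, the literal count and the named test can disagree, always by the count being too strict. At a true PPV of 92% the loss runs from 0.82 to 0.66 at m = 48 and from 0.83 to 0.48 at m = 47, and the count cannot be met at 43 or fewer. This rests on reading the count literally and on m counting only patients with a fluorescent-site biopsy. How often m would fall short is unknown. The low-grade emphasis is supported in direction only, and is tempered by the unresolved role of the probe.

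Separately, and whatever m turns out to be, 44 of 50 does not strictly meet the stated alpha: 0.1034 against 0.10. The excess is small, but removing it by moving to 45 lowers power to 0.79.

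**What to change.** 1. In section 7.2, state the rule per subgroup as the named one-sided exact test (PPV 80%, alpha 0.10) on the m fluorescent-site biopsies, with one alpha convention throughout.
   - Strict alpha of at most 0.10: cut-offs are 45 at m = 50 (restate power as 0.79), 44 at 49, 43 at 48, 42 at 47, 41 at 46, 40 at 45, 40 at 44, 36 at 40, 32 at 35 and 28 at 30. No rejection is possible at 10 or fewer.
   - Otherwise keep 44 of 50, state alpha as 0.103, and apply the same tolerance at every m; for example, 39 at m = 44 (alpha 0.102, power 0.86).
2. Reconcile sections 5.2, 7.1 and 7.3. State whether a patient without a fluorescent-site biopsy leaves the PPV denominator, which agrees with the per-biopsy definition, or counts as a non-success. If the latter, state the lower power: about 0.56 and 0.22 at assumed yields of 95% and 90%. This is the sponsor's choice.
3. In section 7.3, report for each subgroup, beside PPV, the number of patients without such a biopsy, the reason (no fluorescence, or sampling not safe), and the fluorescence rate with an exact 95% CI. This guards against a small m passing unnoticed: 11 of 11 meets the test (0.8^11 = 0.086) although its two-sided 95% CI starts at 71.5%.

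The cost is wording and a short table, with no new data. The change does not restore lost information: with a re-derived cut-off, power is still 0.79 at m = 40, 0.69 at 35 and 0.57 at 30.
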